At least 1 patient representing each of the following pediatric age subsets will be enrolled: birth to 5 years, 6 to 11 years and 12 to < 18 years. However, patients under 2 years of age will only be enrolled after at least 3 pediatric patients older than 2 years of age have been dosed with durvalumab and tremelimumab and have cleared the DLT observation period and have been evaluated by the DRC. Additionally, at least 1 day between first patient and subsequent patients dosed at each DL is required.

Three DLs may be explored in each of the treatment arms (detailed DLs can be seen in [Table](#) , [Table 11](#), [Table 12](#), and [Table 13](#)). The starting doses (DL 1) will be 100% of the recommended adult dose of both durvalumab and tremelimumab administered as weight-adjusted doses. The doses and schedules are as follows:

1. Cycle 1 (durvalumab monotherapy): durvalumab 20 mg/kg
2. Cycles 2 to 5 (durvalumab in combination with tremelimumab): durvalumab 20 mg/kg and tremelimumab 1 mg/kg (4 cycles administered every 28 days)
3. From Cycle 6 onwards, treatment will continue until a discontinuation criterion is met, with durvalumab monotherapy administered at 20 mg/kg every 28 days.

From Cycle 2 onwards, a treatment delay of up to 14 days is permitted between consecutive cycles to manage any side-effects. If a treatment delay of more than 14 days is required, the start of the cycle that had to be delayed must be skipped until the planned Day 1 of the next cycle. No dose reductions are permitted.

[figure not shown]
The pediatric PK will be considered equivalent to the adult PK when the lower limit of the 80% CI of the pediatric exposure (as measured by the area under the plasma drug concentration-time curve from Day 0 to Day 28 [AUC_{0-28}]) is more than 50% of the adult exposure. Adequate exposure will be declared only if $\geq 80\%$ (5 of 6 patients at a dose level) achieve acceptable adult exposure PK, as defined. Durvalumab and tremelimumab will be escalated sequentially with durvalumab first followed by tremelimumab.

The degree of dose escalation at DLs 2 and 3 will be determined based on the review of all the safety and emerging PK data. It is anticipated that dose ranges of 24 to 40 mg/kg and 1.2 to 2 mg/kg for durvalumab and tremelimumab, respectively, will be explored in DLs 2 and 3 (the maximum dose of durvalumab that will be explored is 40 mg/kg).

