4.2 Scientific rationale for study design

The dose-finding phase of the study will be conducted to determine whether adult PK exposure levels can be achieved by the administration of the adult recommended dose of both durvalumab and tremelimumab to pediatric patients. Furthermore, simulations and preliminary PK results from the ongoing CCI study show that children weighing ≥ 35 kg are predicted to have exposure levels consistent with adult patients, whereas children with a body weight < 35 kg are predicted to have approximately 2-fold lower exposure than those observed in adults (Section 4.3.1.1). Overall, 3 DLs may be explored in this study, with 2 arms separated by a cutoff body weight of 35 kg, based on these PK findings.

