4.3 Justification for dose

4.3.1 Durvalumab and tremelimumab dose and treatment regimen justification

4.3.1.1 Durvalumab + tremelimumab combination therapy dose rationale

The durvalumab + tremelimumab combination therapy doses and regimen selected for this study are based on the goal of selecting an optimal combination dose of durvalumab and tremelimumab that would yield sustained CCI demonstrate promising efficacy, and have an acceptable safety profile.

Pharmacokinetics/Pharmacodynamics data

Durvalumab:

Study patients will initially receive the recommended adult weight-adjusted dose of 20 mg/kg IV durvalumab q4w (maximum durvalumab dose to be explored is 40 mg/kg). Based on the simulations and preliminary PK results from study CCI, children ≥ 35 kg are predicted to have exposure levels consistent with adult patients. However, simulations also indicated that patients < 35 kg in weight are expected to have approximately 2 to 10-fold lower exposure than those observed in adults depending on weight. The minimum acceptable AUC_{0-28} for this

pediatric population is 50% of the adult AUC (3233-day \times $\mu\text{g/mL}$). The systemic exposure in children will be considered adequate if the lower 80% confidence bound on estimated AUC_{0-28} at the current DL is higher than 3233-day \times $\mu\text{g/mL}$. If lower exposures are confirmed, escalations defined in Section 4.1.1 will take place, and PK assessments will take place to confirm that exposure levels similar to adults are achieved.

Tremelimumab:

Children and young adults will initially receive the recommended adult weight-adjusted dose of 1 mg/kg IV tremelimumab q4w. Based on the simulations, children ≥ 35 kg are predicted to have exposure levels consistent with adult patients. However, simulations also indicated that patients < 35 kg in weight are expected to have approximately 2 to 4-fold lower exposure than those observed in adults. AUC_{0-28} will be used to determine adequacy of systemic exposure. The minimum acceptable AUC_{0-28} for this pediatric population is 50% of the adult AUC, or 137-day \times $\mu\text{g/mL}$. The systemic exposure will be considered adequate if the lower 80% confidence bound on estimated AUC_{0-28} at the current DL is greater than 137-day \times $\mu\text{g/mL}$. If lower exposures are confirmed, escalations defined in Section 4.1.1 will take place, and new assessments will take place to confirm that exposure levels similar to adults are achieved.

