Drug	Cycle 1	Cycles 2-5	Cycle 6 onwards
Durvalumab	40 mg/kg	40 mg/kg	40 mg/kg
Tremelimumab	NA	2 mg/kg	NA

NA Not applicable.

Table 13 **Planned dose level -1**

Dose Level -1			
Drug	Cycle 1	Cycles 2-5	Cycle 6 onwards
Durvalumab	15 mg/kg	15 mg/kg	15 mg/kg
Tremelimumab	NA	0.75 mg/kg	NA

NA Not applicable.

- **Dose Level 1:** Patients will receive the equivalent adult weight-based dose of both durvalumab and tremelimumab, as listed in [Table](#) .
- **Dose Level 2:** Patients will receive a tremelimumab dose that remains constant to that of DL 1 (1 mg/kg). However, there will be a planned dose escalation for durvalumab to increase the dose to a maximum of 40 mg/kg (reflecting a 100% increase from the starting dose). If data from the PK modeling obtained from patients treated at DL 1 suggests that adequate exposure levels will require less than a doubling of the dose, then an appropriate dose between 24 mg/kg and 40 mg/kg may be evaluated instead of 40 mg/kg. If data from the PK modeling obtained from patients treated at DL 1 suggests that adequate exposure level have not been obtained and a higher dose may be needed to achieve such an exposure, the dose escalation plan may be adjusted to incorporate subsequent dose increases.
 - If at DL 1 durvalumab exposure is adequate and tremelimumab exposure is too low, DL 2 can be skipped and tremelimumab alone will be escalated to DL 3 with durvalumab dosing remaining at the initial dose of 20 mg/kg.
- **Dose Level 3:** Patients will receive adjusted doses of both durvalumab and tremelimumab; the dose of durvalumab will be determined from PK modeling data obtained from DL 2. There will be a planned dose escalation for tremelimumab to increase the dose to 2 mg/kg (reflecting a 100% increase from the starting dose). If data from the PK modeling obtained from patients treated at DL 1 suggests that adequate exposure level will require less than a doubling of the dose, then an appropriate dose between 1.2 mg/kg and 2 mg/kg may be evaluated instead of 2 mg/kg. If data from the PK modeling obtained from patients treated at DL 1 suggests that adequate exposure level have not been obtained and a higher dose may be needed to achieve such an exposure, the dose escalation plan may be adjusted to incorporate subsequent dose increases.

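### The protocol caps durvalumab at 40 mg/kg but the Dose Level 2 text allows further increases with no ceiling, and it gives the predicted exposure shortfall below 35 kg as about 2-fold in one section and 2 to 10-fold in the section that it cites

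*Protocol*

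**What the plan says.** **Durvalumab dose range.** Protocol 4.1.1 sets the starting dose ("Cycle 1 (durvalumab monotherapy): durvalumab 20 mg/kg") and a limit: "the maximum dose of durvalumab that will be explored is 40 mg/kg". Protocol 4.3.1.1 repeats the limit: "maximum durvalumab dose to be explored is 40 mg/kg". The notes to the Synopsis dose-level figure, to protocol Figures 1 and 2 and to SAP Figure 1 also call 40 mg/kg the maximum at Dose Levels (DLs) 2 and 3, and mention only lower alternatives.

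In protocol 6.1.1.1 the DL 2 text plans to "increase the dose to a maximum of 40 mg/kg (reflecting a 100% increase from the starting dose", and offers a dose between 24 and 40 mg/kg if less than a doubling is enough. It then takes the case in which DL 1 exposure was inadequate and "a higher dose may be needed to achieve such an exposure, the dose escalation plan may be adjusted to incorporate subsequent dose increases". No upper limit is attached. The same sentence recurs under DL 3, after the tremelimumab text.

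**Predicted shortfall.** Protocol 4.2 supports the three levels and the 35 kg split by saying that children below 35 kg "are predicted to have approximately 2-fold lower exposure than those observed in adults", and points to 4.3.1.1. That section says that such patients are "expected to have approximately 2 to 10-fold lower exposure than those observed in adults depending on weight" for durvalumab. For tremelimumab it gives about 2 to 4-fold.

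**Exposure rule.** Protocol 4.3.1.1 sets the minimum AUC over 28 days at 50% of the adult value: 3233 day × µg/mL for durvalumab and 137 for tremelimumab, judged on a lower 80% confidence bound. Protocol 4.1.1 calls a dose level adequate when 5 of 6 patients qualify.

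**Patient numbers.** The protocol Synopsis, protocol 9.2 and SAP 1.3 give 36 evaluable patients if all three levels run in both weight arms, and a maximum of 45 after replacement of about 20%.

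**The concern.** Two pairs of statements do not agree, and both bear on the primary dose-finding question of whether adult-equivalent exposure can be reached.

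The first pair concerns the top of the durvalumab range. A cap stated in several places stands beside a permission to go on increasing. A site, an ethics committee or the Data Review Committee could read the protocol either way on whether a dose above the stated maximum may be given to a child.

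The second pair concerns the reason for the range. A doubling of the starting dose is a sensible span for a 2-fold shortfall. It is a different proposition if the shortfall runs to 10-fold. Section 4.2 carries forward only the mildest value from the section that it cites.

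The two are linked. If the wider prediction applies, inadequate exposure at the cap becomes likely, and that is when it matters whether the cap binds. Protocol Table 8 sends a tolerated but under-exposed level to the next level, and no level after DL 3 is defined.

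**Working it through.** **Inputs.** Starting dose 20 mg/kg and cap 40 mg/kg (protocol 4.1.1); minimum AUC 3233 day × µg/mL, equal to 50% of adult (4.3.1.1); shortfall F of about 2 (4.2) or 2 to 10 (4.3.1.1).

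**1. The plan's own figure.** Section 6.1.1.1 describes 40 mg/kg as a 100% increase. (40 − 20)/20 = 1.00, so it reproduces. The capped range is a factor of 2.

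**2. Implied adult AUC.** 3233/0.5 = 6466.

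**3. Exposure at the start and at the cap.** At 20 mg/kg the predicted AUC is 6466/F. At 40 mg/kg it is 2 × 6466/F if exposure is proportional to dose. That proportionality is my assumption.

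| Shortfall F | AUC at 20 mg/kg | AUC at 40 mg/kg | % of adult at 40 mg/kg | Above 3233? |
|---|---|---|---|---|
| 2 | 3233 | 6466 | 100% | yes |
| 3 | 2155 | 4311 | 67% | yes |
| 4 | 1616 | 3233 | 50% | no, equal to it |
| 5 | 1293 | 2586 | 40% | no |
| 10 | 647 | 1293 | 20% | no |

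The condition 2 × 6466/F > 3233 gives F < 4. At F = 10, exposure would have to rise 5-fold just to equal the minimum, against a 2-fold rise in dose.

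**4. Allowing for the confidence bound.** The table uses point estimates. Reading the rule at group level with n = 6, the lower bound is the geometric mean × exp(−t·s/√6), where s = √ln(1 + CV²). The documents give no CV; I assume 20% to 50%. With a two-sided 80% interval the bound is 0.888 to 0.752 of the mean, so the largest shortfall that passes at the cap is 4 × 0.888 = 3.6 down to 4 × 0.752 = 3.0. With a one-sided 80% bound the factors are 0.928 to 0.838, giving 3.7 down to 3.4.

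**5. Tremelimumab.** Implied adult AUC is 137/0.5 = 274. A 4-fold shortfall at 2 mg/kg gives 2 × 274/4 = 137, again equal to the minimum and not above it.

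**6. Patient numbers.** One level in both arms takes 12 patients, so 6 per level and arm. 3 levels × 2 arms × 6 = 36, and 36/0.80 = 45, which reproduces. One further level in one arm would make 42 evaluable, and 42/0.80 = 52.5, which is above the stated maximum of 45.

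**The case against.** **The two dose statements can be read together.** The DL 2 permission names no dose above 40 mg/kg. Taken alone, a dose higher than DL 1 could still lie between 24 and 40 mg/kg, and the specific cap could be held to limit a general permission to adjust the plan. A reader might infer that the two texts flatly exclude each other. The documents do not go that far. But the sentence follows the 24 to 40 mg/kg option as its counterpart, so going past the cap is its most natural reading, and the ambiguity stands.

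**The DL 3 copy adds nothing on durvalumab.** It follows the tremelimumab text, and the explicit limits in 4.1.1 and 4.3.1.1 cover durvalumab only. This is correct; the conflict rests on the DL 2 text.

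**Adequacy is not judged by weight band.** A reader might infer that the smallest children cannot reach the target, or that no recommended dose can be declared for them. The documents do not support this. Adequacy needs 5 of 6 patients at a dose level, so one very small child can fall short and the level still pass. SAP 1.2 takes the recommended dose from the weight arms. The weights at which the shortfall passes 4-fold are not given, so the affected children cannot be counted.

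**The shortfalls are predictions.** They come from simulation, and 4.3.1.1 makes escalation depend on their being confirmed. Dose proportionality is not stated either. Both limit the arithmetic, but neither removes the disagreement between 4.2 and 4.3.1.1.

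**The sample size is already conditional.** Protocol 9.2 ties the final number to the levels explored. That answers the figure of 36. The stated maximum of 45 remains exposed, though the intermediate levels allowed in 4.1.1 strain it in any case.

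**Escalation may be over.** The version history refers to results from the dose-finding phase, which suggests that the decision has passed. If so, the practical weight shifts to how the dose range and its basis are reported.

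**Conclusion.** The point holds as two inconsistencies in the current protocol text. The durvalumab cap in 4.1.1, 4.3.1.1 and the DL 2 text conflicts with the most natural reading of the further-increase provision in that same DL 2 text. The shortfall in 4.2 does not match the section that it cites: about 2-fold against 2 to 10-fold for durvalumab and 2 to 4-fold for tremelimumab.

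The size depends on which shortfall is meant. Assuming dose-proportional exposure, the capped range exceeds the 50% minimum only for shortfalls below 4-fold on point estimates, or below about 3.0 to 3.7-fold with the lower bound, n = 6 and the assumed CVs. It is therefore enough under the 4.2 figure and not enough across the 4.3.1.1 range. The documents do not establish which shortfall figure or which dose statement is right. The correction should be made because it concerns a pediatric dose ceiling and the stated reason for the escalation range.

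**What to change.** 1. Reconcile protocol 4.1.1, 4.3.1.1, the figure notes (Synopsis, Figures 1 and 2, SAP Figure 1) and the DL 2 text in 6.1.1.1, so that one statement governs the durvalumab dose range.
2. Reconcile protocol 4.2 and 4.3.1.1 on the predicted shortfall below 35 kg, naming the drug to which each figure applies.
3. Make the maximum of 45 in the Synopsis, protocol 9.2 and SAP 1.3 consistent with the number of dose levels that the reconciled text allows.

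The cost is protocol and SAP wording. If dose finding is complete, the same clarification belongs in the study report. No dose limit, exposure figure or rule for the recommended dose is proposed here.

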6.1.1.2 Dose-expansion phase

Patients will be treated with the combination of durvalumab and tremelimumab using the RP2D of each agent, based on data obtained from the dose-finding phase. Durvalumab and tremelimumab will be administered concurrently on an every 28-day (4 weeks) cycle for a total of 4 cycles (Cycles 1 to 4); subsequently, durvalumab is continued on an every 28-day cycle as monotherapy until clinical or confirmed PD, or other discontinuation criteria is met, whichever comes first.

However, if in the opinion of the Investigator, a patient received clinical benefit from treatment with the combination of durvalumab and tremelimumab and subsequently progressed whilst on durvalumab maintenance monotherapy, such patients may restart treatment with the combination of durvalumab and tremelimumab for 4 cycles. A patient who meets these criteria should be reconsented and receive another 4 cycles of tremelimumab while continuing durvalumab treatment. Retreatment with an additional combination regimen may only occur once (for a single time).

6.1.2 Study Drug Administration

During Cycles 1 and 2 of the dose-finding phase, durvalumab is infused over 120 minutes (2 hours). Starting with Cycle 3, if tolerated, the durvalumab infusion time may be reduced to 60 minutes (1 hour). Tremelimumab infusions will be administered over 60 minutes (1 hour) during all treatment cycles.

- During the dose-expansion phase, all durvalumab infusions will be administered over 60 minutes (1 hour)

On days when both durvalumab and tremelimumab are scheduled (Cycles 2 to 5 in dose-finding phase and Cycles 1 to 4 in dose-expansion phase), the tremelimumab infusion is to be administered *first* followed by a 1-hour interval (maximum 2 hours) before the start of the durvalumab infusion.

- Refer to Section 8.2.3 (Vital signs) for details on required vital signs and observation periods

Both durvalumab and tremelimumab infusions are to be administered using a 0.2 or 0.22 µm low-protein binding in-line filter.

No other drugs are to be infused through the same line or port while study infusions are being administered.

The IV tubing is flushed with a volume of saline equal to the priming volume of the administration set used after the contents of the IV bag or IV syringe are fully administered, according to institutional policy to ensure the full dose is administered.

The study infusion may be interrupted for an infusion reaction and when permitted, is restarted at a slower (ie, 50%) infusion rate. In instances where the total dose cannot be completed using an 8 hour hang time, a new infusion bag must be prepared to complete the study infusion.

6.1.3 Study Drug Preparation

AstraZeneca will supply durvalumab (MEDI4736) and tremelimumab to be used according to [Table 14](#).

Table 14 Study treatments

	Treatment 1	Treatment 2
Study treatment name	Durvalumab (MEDI4736)	Tremelimumab
Dosage formulation:	500- or 120-mg vial solution (50 mg/mL)	400- or 25-mg vial solution (20 mg/mL)
Route of administration	IV	IV
Dosing instructions:	Section 6.1.1.1 (dose-finding). Section 6.1.1.2 (dose-expansion).	Section 6.1.1.1 (dose-finding). Section 6.1.1.2 (dose-expansion).
Packaging and labeling	Study treatment will be provided in 500- or 120-mg vials. Each vial will be labeled in accordance with GMP Annex 13 and per country regulatory requirement. ^a	Study treatment will be provided in 400- or 25-mg vials. Each vial will be labeled in accordance with GMP Annex 13 and per country regulatory requirement. ^a
Provider	AstraZeneca	AstraZeneca

^a Label text prepared for durvalumab (MEDI4736) will show the product name as “MEDI4736” or “durvalumab (MEDI4736)” depending upon the agreed product name used in the approved study master label document. All naming conventions are correct during this transitional period. GMP Good Manufacturing Practice, IV intravenous.

For patients >20 kg, both durvalumab and tremelimumab doses can be prepared and administered either by an infusion bag or as a syringe, according to local practices. For patients ≤20 kg, doses should be prepared in a syringe with suggested final volumes based on weight ranges, as listed in Table 15, and administered via a syringe pump.

Table 15 Syringe administration volumes for patients ≤20 kg

Weight (kg)	Total syringe volume range (mL)
2.4–5.0	15
5–10	15–20
10–15	20–30
15–20	30–50

6.1.3.1 Durvalumab (MEDI4736)

Durvalumab is supplied by AstraZeneca as a 500- or 120-mg vial formulated as solution containing 50 mg/mL durvalumab, 26 mM histidine/histidine-hydrochloride, 275 mM trehalose dihydrate, and 0.02% weight/volume (w/v) polysorbate 80; the final pH of the solution is 6.0. The nominal fill volume is 10.0 mL for the 500-mg vial and 2.4 mL for the 120-mg vial. Investigational product vials are stored at 2°C to 8°C (36°F to 46°F) and must not be frozen. Drug product should be kept in the original packaging until use to prevent prolonged exposure to light.

The starting DL, using a weight-based approach, will be 20 mg/kg; during the dose-finding phase, 2 additional DLs of durvalumab will be evaluated (Table , Table 11, and Table 12). The patient's weight at baseline is to be used for subsequent treatment dosing calculations unless there is a $\geq 10\%$ change in the measured weight. The dose will be prepared using an IV bag (polyvinyl chloride [PVC] or non-PVC) or a syringe, according to local practices, and administered via a standard infusion or syringe pump.

The dose of durvalumab for administration must be prepared by the Investigator's or site's pharmacist (or designee) using aseptic technique. Total time from needle puncture of the durvalumab vial to the start of administration should not exceed:

- 24 hours at 2°C to 8°C (36°F to 46°F)
- 4 hours at room temperature.

The durvalumab vial size (120 mg or 500 mg) should be selected based on: 1) availability and 2) calculated durvalumab dose volume. It is recommended that for small durvalumab volumes (2.4 mL or less), the 120-mg vial size may be used; and for larger volumes (greater than 2.4 mL), the 500-mg vial size may be used. A combination of vial sizes may be used depending on the dose volume in order to minimize drug wastage (eg, for a dose volume of 11.0 mL, one 500 mg and one 120 mg vial may be used).

Durvalumab will be diluted in 0.9% sodium chloride (normal saline [NS]) to a final concentration between 1 and 20 mg/mL, and administered with IV tubing containing a 0.2 μm or 0.22 μm low-protein binding in-line filter; acceptable configurations include an IV set containing an in-line filter or the attachment of a separate filter to the distal end of the IV tubing.

Preparation of durvalumab doses for administration with an IV bag

Intravenous bag preparation

Dose calculation

The volume (in mL) of durvalumab to be added to an IV bag containing 0.9% sodium chloride is calculated as follows:

Dose level (mg/kg) \times patient weight (kg) / 50 (mg/mL of durvalumab)

Example:

- Dose: 20 mg/kg
- Patient weight: 80 kg
- Dose for patient: $20 \text{ (mg/kg)} \times 80 \text{ (kg)} = 1600 \text{ (mg)}$
- Dose volume: $1600 \text{ (mg)} / 50 \text{ (mg/mL)} = 32.0 \text{ mL}$
- Add the durvalumab dose volume into an infusion bag (PVC or non-PVC) containing 0.9% sodium chloride (NS); mix the solution using gentle inversion. Do not shake.
- Final products are prepared at a concentration between 1 and 20 mg/mL.
- Infusions should be administered immediately after preparation; however, once prepared, infusions can be stored for up to 24 hours under refrigeration and 4 hours at room temperature. Once the infusion has started, the hang-time of the infusion should not exceed 8 hours.
- Sites are to follow local practices for final IV bag preparation, including attachment of IV tubing (PVC or non-PVC) and priming (if applicable), and to ensure the IV infusion set connected to the IV infusion bag contains a 0.2 or 0.22 μm low-protein binding in-line filter.

Preparation of durvalumab doses for administration with an IV syringe

Intravenous syringe preparation

The volume (in mL) of durvalumab to be added to an IV syringe containing 0.9% sodium chloride is calculated as follows:

Dose level (mg/kg) \times patient weight (kg) / 50 (mg/mL of durvalumab)

Example:

- Dose: 20 mg/kg
- Patient weight: 10 kg
- Dose for patient: $20 \text{ (mg/kg)} \times 10 \text{ (kg)} = 200 \text{ (mg)}$
- Dose: $200 \text{ (mg)} / 50 \text{ (mg/mL)} = 4.0 \text{ mL}$
- Withdraw the durvalumab dose volume into a suitable size syringe. Prepare a separate syringe containing required amount of sodium chloride 0.9% (NS) to achieve the total syringe volume.

- Transfer the durvalumab solution into the NS syringe; once capped (or secured with an attached needle), mix the solution using a gentle inversion. Do not shake.
- Final products are prepared at a concentration between 1 and 20 mg/mL.
- Infusions should be administered immediately after preparation; however, once prepared, infusions can be stored for up to 24 hours (refrigeration) and 4 hours (room temperature). Once the infusion has started, the hang-time of the infusion should not exceed 8 hours.
- Sites are to follow local practices for final preparation, including attachment of IV tubing (PVC or non-PVC) and priming (if applicable), and to ensure the IV administration set connected to the IV syringe contains a 0.2 or 0.22 µm low-protein binding in-line filter.

